Statistical Methods	
Sample Size:
 
For the primary efficacy endpoint of proportion of subjects with at least one CSE, assuming a 20% true rate of at least one CSE, two-sided 5% Type 1 error and 80% power, the sample size to rule out a CSE rate less than or equal to 10% requires 86 evaluable subjects in the primary analysis group. The trial will have met the primary endpoint if at least 15/86 (17.4%) subjects have at least one CSE. The 95% two-sided Clopper-Pearson exact confidence bound at 17.4% is (10.1%, 27.1%).
 
Efficacy
 
A descriptive analysis of the baseline subject and tumor characteristics will be performed. Quantitative data will be presented as a standard set of summary statistics (n/mean (standard deviation)/median/minimum/maximum). Categorical data will be expressed as frequency (%).
 
For the primary endpoint analysis, the proportion of subjects undergoing NIR imaging with at least 1 CSE will be identified and tested under the following null hypothesis:
 
Ho: $P \leq 0.10$
 
The alternative hypothesis states that the proportion of subjects undergoing NIR imaging with at least 1 CSE will be greater than the chosen margin of 0.10:
 
Ha: $P > 0.10$
 
At 86 evaluable subjects, this trial is power at 80% to reject the null hypothesis of a 10% or fewer of subjects experiencing at least one CSE. Two-sided 95% exact confidence intervals for the proportion of subjects with at least one CSE will be constructed.
 
For the secondary endpoint analysis sensitivity, PPV, and 1-PPV will be calculated and presented along with 95% confidence intervals using GEE model analysis to factor in within-subject correlation for subjects with multiple tumors.
 
Safety:
 
Adverse event (AE) data will be listed by subject. Treatment-emergent adverse events (TEAEs), serious adverse events (SAEs), and AEs leading to study drug discontinuation will be summarized by system organ class and preferred term using the current version of the Medical Dictionary for Regulatory Activities (MedDRA).
 
Listings of individual subject laboratory results will be provided. Laboratory results, Clinically Significant and change from baseline for selected lab tests will be summarized by treatment at scheduled visits.
 
Twelve-lead ECGs and vital signs measurements will be listed by subject and summarized by incidence of events/abnormalities or descriptive statistics as appropriate. Individual data for physical examination findings, prior and concomitant medications and medical history will be provided.

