2. STUDY OBJECTIVE AND ENDPOINTS

2.1 Objectives:

2.1.1 Primary Efficacy Objective:

Assess the efficacy of VGT-309 with near-infrared (NIR) imaging for lesion visualization when compared to standard surgical techniques in subjects undergoing surgery for proven or suspected cancer in the lung.

2.1.2 Secondary Efficacy Objective:

Assess the utility of VGT-309 with NIR imaging to identify cancerous tissue as confirmed by histopathology.

2.1.3 Safety Objective:

Determine the safety and tolerability of VGT-309 in subjects with proven or suspected cancer in the lung.

2.2 Endpoints:

2.2.1 Primary Efficacy Endpoint:

Identify the proportion of subjects with at least one Clinically Significant Event (CSE) as defined by:

- A. Intraoperative localization of one or more preoperatively identified lung lesions using VGT-309 with NIR imaging when standard surgical techniques using white light and/or palpation failed to identify the lesion(s), and lesion(s) are confirmed by histologic examination to be other than normal lung tissue.
- B. Identification of one or more synchronous or occult lung lesions using VGT-309 with NIR imaging when standard surgical techniques using white light and/or palpation and preoperative imaging failed to identify the lesion(s), and lesion(s) are confirmed by histologic examination to be cancerous or precancerous.
- C. Identification of fluorescence within ≤ 10 mm from the inside edge of the closest staple line as measured by the investigator *ex vivo* in the operating room using NIR imaging, with pathologic margin confirmed by histologic examination to be ≤ 10 mm.
NOTE: Margins from excisions of known or suspected metastases at the time of the surgery, OR diagnostic wedge resections where a completion lobectomy or segmentectomy was subsequently performed, will not be considered for Margin CSE inclusion.
- D. Identification of lymph nodes by VGT-309 with NIR imaging confirmed by histologic examination to be cancerous.

2.2.2 Secondary Efficacy Endpoints:

To evaluate the sensitivity, positive predictive value (PPV), and 1-PPV of VGT-309 with NIR imaging for lesion(s) *in vivo*:

- 1. Sensitivity is defined as the probability that the tissue fluoresces when it is cancer, as confirmed by histology $(TP/(TP+FN))$ *
- 2. Positive predictive value (PPV) is defined as the probability that a tissue sample contains cancer on histologic exam if it fluoresces $((TP/(TP+FP))$ *

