### 9.4.2. Analysis Methods for Secondary Efficacy Endpoints

For the secondary endpoint analyses, sensitivity, PPV, and 1-PPV will be calculated and presented along with 95% confidence intervals for lesions and lymph nodes using *in vivo* assessments. Modeled point estimates and confidence intervals will be reported to account for the multiple dependent observations within subjects using Generalized Estimating Equations (GEE) since only between-subject observations can be modelled as independent. To account for the multiple dependent observations within a subject, the GEEs will be fit in SAS with an independent covariance matrix and binary (logit) outcomes. See Appendix 2.

Raw counts (%) will also be provided.

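### The logit GEE in SAP 9.4.2 gives no usable interval when all contributing tissues agree, and may under-cover if lymph nodes are analysed separately in few subjects; the readable text gives no fallback.

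*Protocol*

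**What the plan says.** The protocol synopsis (Statistical Methods, Efficacy) has sensitivity, PPV and 1-PPV "presented along with 95% confidence intervals using GEE model analysis to factor in within-subject correlation for subjects with multiple tumors". Protocol 10.3.2 repeats this. SAP 9.4.2 widens the scope: the measures are "calculated and presented along with 95% confidence intervals for lesions and lymph nodes", from in vivo assessments. It fixes the model as follows: "the GEEs will be fit in SAS with an independent covariance matrix and binary (logit) outcomes". It refers to Appendix 2 and adds that raw counts and percentages will be shown.

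The readable text does not say:
- whether lesions and nodes are analysed separately or pooled;
- how the standard error is formed, or which quantile is used;
- what is reported when the estimate is 0% or 100%.

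Two other passages bear on how many subjects can contribute. Item D of the primary endpoint (Protocol 2.2.1) is "Identification of lymph nodes by VGT-309 with NIR imaging confirmed by histologic examination to be cancerous". The sample size is planned "assuming a 20% true rate of at least one CSE" and "requires 86 evaluable subjects in the primary analysis group".

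**The concern.** A sandwich-based GEE interval relies on many independent subjects. Lung lesions supply them, because nearly every evaluable subject has at least one. Cancerous lymph nodes may occur in far fewer subjects, and several may come from the same subject. With few subjects and unequal node counts, the sandwich variance tends to be too small, so the interval looks more precise than it is.

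The second problem does not depend on any assumption about numbers. On the logit scale an estimate of 0% or 100% has no finite value, so the model returns no usable limits. At 100% the lower limit is what a reader most wants. If the plan has no fallback, one would have to be chosen after the result is known.

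These measures are the only secondary efficacy endpoints. No test or success threshold is attached to them, so what is at stake is honest reporting of precision, not a trial decision.

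**Working it through.** **1. The plan's own figure.** Inputs from the synopsis: "assuming a 20% true rate of at least one CSE, two-sided 5% Type 1 error and 80% power", against a null rate of 10%. The normal approximation gives

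n = [1.960·√(0.10·0.90) + 0.8416·√(0.20·0.80)]² / (0.20 − 0.10)² = (0.5880 + 0.3366)² / 0.01 = 85.5, so 86.

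The exact 95% interval for 15/86 is 10.1% to 27.1%, as stated. The 86 and the 20% can therefore be used as inputs.

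**2. How many subjects contribute to the nodal measures.** A node that fluoresces and is histologically cancerous meets item D, which does not require that standard technique failed. Every subject with an in vivo true-positive node is therefore a subject with an event. At the planning rate, 0.20 × 86 = 17.2 subjects have any event, so about 17 at most have a true-positive node, and fewer if items A to C supply some of the events.

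This is not the number contributing to each measure:
- Sensitivity uses TP + FN, so subjects with only missed cancerous nodes are added. With one node per subject and sensitivity 0.5, 17 true-positive subjects imply 17/0.5 = 34 contributors; at 0.7, 17/0.7 = 24.
- PPV and 1-PPV use TP + FP, so subjects with only false-positive nodes are added. The event rate does not bound that number.

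**3. The interval checked.** For an intercept-only logit GEE under independence, the point estimate p is the pooled proportion. The SAP does not state the standard error or the quantile; an uncorrected sandwich with 1.96 is assumed. With y(i) positive out of n(i) tissues in subject i, and N tissues in all:

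logit(p) ± 1.96 · √Σ[y(i) − n(i)p]² / [N p(1 − p)].

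At p = 0 or 1 the logit is infinite and the denominator is zero. A fitted GEE on such data diverged, with separation warnings.

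**4. Coverage under assumed node counts.** Outcomes are beta-binomial. The table uses within-subject correlation 0.3 and skewed node counts. The first three columns give coverage where an interval exists, at true sensitivity 0.5. The last gives the share of trials with no interval at true sensitivity 0.9.

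| Contributing subjects | Mean 2 nodes | Mean 3 nodes | Mean 5 nodes | No interval (0.9, mean 3) |
|---|---|---|---|---|
| 5 | 90.6% | 85.4% | 81.0% | 36% |
| 9 | 91.6% | 88.7% | 86.9% | 16% |
| 13 | 92.0% | 90.7% | 88.9% | 7% |
| 17 | 92.7% | 91.9% | 90.3% | 3% |

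Other settings:
- 1 to 12 uneven nodes (mean 3.2), 6 to 17 subjects, sensitivity 0.5-0.8: 84-91%.
- 1 to 3 nodes per subject: about 90-95% with 5 subjects and 94-96% with 17.
- Whole grid (5 to 17 subjects, correlation 0.1-0.5, true rate 0.3-0.9): 81-97%, with medians of 90% at 5 subjects, 92% at 9 and 93% at 13 and 17.
- Lesions, 60 to 80 subjects: about 95-97%. At a true value of 98%, however, no interval exists in 15-25% of trials.

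**5. The alternative.** A Korn-Graubard interval (Clopper-Pearson on a design-effect-adjusted sample size, subject as cluster) covered about 93-99% in the settings tried. This includes Clopper-Pearson on the K contributing subjects at 0% or 100%. At 100% its lower limit is 0.025^(1/K): 54% for K = 6, 69% for K = 10, 80% for K = 17.

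**The case against.** A reader might infer that the nodal analysis can have only about 5 to 17 subjects, and that its nominal 95% intervals therefore cover only 85-91%. The documents do not support this. Seventeen bounds only subjects with a true-positive node, and only at a planning rate that is not a ceiling. The lower figure of 5 comes from no passage. Missed-node subjects add to sensitivity, and false-positive subjects add to PPV. The coverage range needs several unequal nodes per subject, and no document gives node numbers. With few nodes each, coverage is mostly above 90%.

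Three further objections have force:
- The secondary endpoint is defined for lesions, and pooling nodes with them is not excluded. If they are pooled, contributors approach 86 and the coverage problem largely goes away.
- Appendix 2 may already specify a correction or a fallback. It is unreadable here, so its absence cannot be asserted.
- Raw counts will be shown, so a 100% result would not be hidden. Counts alone, however, supply no interval.

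The Korn-Graubard interval is also not the only remedy. A t quantile on K − 1 degrees of freedom, with the standard error multiplied by √(K/(K − 1)), restored coverage to about 95-100% where an interval exists. It does nothing at 0% or 100%, so a boundary rule is needed in either case.

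**Conclusion.** The point holds in a limited form. The failure at 0% or 100% is a property of the logit GEE and needs no assumption about node numbers. How often it occurs does: at true sensitivity 0.9 with uneven node counts, roughly 28-39% of trials with 6 contributing subjects and 3-7% with 17. It can also affect lesions if the true value is near 98%.

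Under-coverage for nodes is conditional on a separate nodal analysis, an uncorrected sandwich interval with a normal quantile, and few contributing subjects. On those terms coverage is about 84-96% in most settings tried, falling to 81% with 5 subjects and many uneven nodes. More contributors do not fully remove it: with 25 subjects and skewed counts, coverage at sensitivity 0.5-0.8 is still 91-92%. Lesion intervals are otherwise adequate.

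This is an inexpensive improvement worth making before database lock. It does not affect the primary analysis.

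**What to change.** Amend SAP 9.4.2, unless Appendix 2 already covers these points. The protocol need not change, because its Section 10 lets the SAP govern where methods differ.

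1. Keep the GEE point estimate; under independence it equals the pooled proportion.
2. Report lesions and lymph nodes separately, with the number of contributing subjects beside each estimate.
3. Replace the interval with a cluster-adjusted Clopper-Pearson (Korn-Graubard) 95% interval with subject as the cluster, for example SAS PROC SURVEYFREQ with a CLUSTER statement and CL(TYPE=CP).
4. At 0% or 100%, use Clopper-Pearson with the number of contributing subjects as n.

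The cost is SAP wording and one different SAS procedure, with no new data. Node intervals become wider: with 10 subjects, sensitivity 0.7 and correlation 0.3, the mean width is 0.49 instead of 0.39, about a quarter more (0.49/0.39 = 1.26). Exact limits already serve the primary endpoint, so the approach fits the plan.

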1. INTRODUCTION

A comprehensive review of VGT-309 is contained in the Investigator's Brochure supplied by the Sponsor, Vergent Bioscience, Inc. The Investigator's Brochure should be reviewed prior to initiating the study.

1.1 Background and Rationale

Non-small cell lung cancer (NSCLC) is a particularly lethal cancer for which the best opportunity for cure comes from early detection and complete resection at surgery. Great advances in minimally invasive surgery (robotics; video-assisted thoracic surgery) have provided the opportunity to reduce the impact of major lung resection on the subject with lung cancer.

Minimally invasive surgery has come at the cost of increasing difficulty in localizing small cancers deep in the lung parenchyma due to the elimination of the ability to palpate the lung through a large thoracotomy incision. Currently this is overcome by one of three methods: a) remove a larger amount of tissue than required for biopsy of a suspicious lesion; b) wait until a suspicious lesion has grown sufficiently to allow easier detection at surgery; or c) perform a thoracotomy.

None of these options is optimal. The first, because a large amount of lung may be unnecessarily removed if the lesion is not cancer; the second, because the opportunity for early curative surgery may be missed if the cancer spreads in the months waiting for it to grow further; and the third negates the proven benefit of minimally invasive surgery.

The use of a tumor-targeted, activatable fluorescent imaging agent that can be taken up and bound by cancer tissues and visualized by tumor-specific fluorescence under NIR light during the surgical procedure could solve this problem if the drug readily identified the lesion for the surgeon. This could allow early and well-targeted surgical biopsy and subsequent appropriate cancer surgery for the correctly identified population.

1.2 Nonclinical *In Vitro* and *In Vivo* Experience

[REDACTED]

1.2.1 Genotoxicity

[REDACTED]

1.2.2 Safety Pharmacology

[REDACTED]

1.2.3 Local Tolerance

[REDACTED]

1.2.4 Single Dose Toxicity in Sprague-Dawley Rats and Beagle Dogs

[REDACTED]

[REDACTED]

[REDACTED]	[REDACTED]	[REDACTED]	[REDACTED]
[REDACTED]	[REDACTED]	[REDACTED]	[REDACTED]
[REDACTED]	[REDACTED]	[REDACTED]	[REDACTED]
[REDACTED]	[REDACTED]	[REDACTED]	[REDACTED]
[REDACTED]	[REDACTED]	[REDACTED]	[REDACTED]

[REDACTED]

[REDACTED]

[REDACTED]

[REDACTED]

[REDACTED]

Refer to the Investigator's Brochure for further details.

2. STUDY OBJECTIVE AND ENDPOINTS

2.1 Objectives:

2.1.1 Primary Efficacy Objective:

Assess the efficacy of VGT-309 with near-infrared (NIR) imaging for lesion visualization when compared to standard surgical techniques in subjects undergoing surgery for proven or suspected cancer in the lung.

2.1.2 Secondary Efficacy Objective:

Assess the utility of VGT-309 with NIR imaging to identify cancerous tissue as confirmed by histopathology.

2.1.3 Safety Objective:

Determine the safety and tolerability of VGT-309 in subjects with proven or suspected cancer in the lung.

2.2 Endpoints:

2.2.1 Primary Efficacy Endpoint:

Identify the proportion of subjects with at least one Clinically Significant Event (CSE) as defined by:

- A. Intraoperative localization of one or more preoperatively identified lung lesions using VGT-309 with NIR imaging when standard surgical techniques using white light and/or palpation failed to identify the lesion(s), and lesion(s) are confirmed by histologic examination to be other than normal lung tissue.
- B. Identification of one or more synchronous or occult lung lesions using VGT-309 with NIR imaging when standard surgical techniques using white light and/or palpation and preoperative imaging failed to identify the lesion(s), and lesion(s) are confirmed by histologic examination to be cancerous or precancerous.
- C. Identification of fluorescence within ≤ 10 mm from the inside edge of the closest staple line as measured by the investigator *ex vivo* in the operating room using NIR imaging, with pathologic margin confirmed by histologic examination to be ≤ 10 mm.
NOTE: Margins from excisions of known or suspected metastases at the time of the surgery, OR diagnostic wedge resections where a completion lobectomy or segmentectomy was subsequently performed, will not be considered for Margin CSE inclusion.
- D. Identification of lymph nodes by VGT-309 with NIR imaging confirmed by histologic examination to be cancerous.

2.2.2 Secondary Efficacy Endpoints:

To evaluate the sensitivity, positive predictive value (PPV), and 1-PPV of VGT-309 with NIR imaging for lesion(s) *in vivo*:

- 1. Sensitivity is defined as the probability that the tissue fluoresces when it is cancer, as confirmed by histology $(TP/(TP+FN))$ *
- 2. Positive predictive value (PPV) is defined as the probability that a tissue sample contains cancer on histologic exam if it fluoresces $((TP/(TP+FP))$ *
- 3. One minus Positive predictive value (1-PPV) is defined as the probability that a tissue sample does not contain cancer when it fluoresces $((FP/(TP+FP))^*$

* TP = true positive, FP = false positive, FN = false negative

[REDACTED]

2.2.4 Safety Endpoints:

Assessment of clinical laboratory tests, physical exam results, ECGs and vital sign measurements at various time points during the study, and documentation of treatment-emergent adverse events.

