5.2 Inclusion Criteria

In order to be enrolled in the study, the subject must:

1. Be willing and able to sign the informed consent and comply with study procedures.
2. Be at least 18 years of age.
3. Meet the following conditions:
 - a. Female participants must be of non-childbearing potential, or,
 - b. If of childbearing potential be non-pregnant or non-lactating and agree to use highly effective contraception from screening through Day 30 after treatment.
 - c. Male participants, if not surgically sterilized, and if engaging in sexual intercourse with a female partner of childbearing potential, must be willing to use highly effective contraception from screening through 30 days post-dose and agree not to donate semen during this waiting period.
 - d. Highly effective contraception involves the use of a condom for the male, plus one of the following for the female:
 - Oral, injectable, implantable, intravaginal, or transdermal hormonal contraceptives, or
 - Intrauterine device or intrauterine hormone-releasing system.

NOTE: Subjects who abstain from heterosexual intercourse as their usual and preferred lifestyle, will not be required to use contraception as described above. They are required to maintain abstinence from screening through Day 30.

NOTE: Subjects in a same sex relationship, must use a barrier form of contraception (e.g., condom, diaphragm) to protect against the transfer of the study drug in any bodily fluids.

4. Have a lung nodule or mass that might be considered primary lung cancer or lung metastases, whether or not it is biopsy-proven prior to surgery.
5. Be scheduled to undergo standard of care surgical resection for a lung nodule or mass with diagnostic and/or curative intent.
6. Have acceptable kidney and liver functions at study entry as evidenced by:
 - a. $ALT/AST \leq 1.5$ times the upper limit of normal,
 - b. Calculated Creatinine Clearance ($CrCl$) ≥ 50 ml/min (manual calculation using Cockcroft-Gault equation),
 - c. Total bilirubin ≤ 1.5 times the upper limit of normal.
7. Have an ECOG score of 0-2.
8. Meet all standard surgical and general anesthesia requirements.
9. Have not participated in an interventional clinical trial within the last 30 days (participation in a disease registry or quality of life study is not exclusionary).

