## 3. STUDY ENDPOINTS

### 3.1. Primary Efficacy Endpoint

Identify the proportion of subjects with at least one Clinically Significant Event (CSE) as defined by:

1. Intraoperative localization of one or more preoperatively identified lung lesions using VGT-309 with NIR imaging when standard surgical techniques using white light and/or palpation failed to identify the lesion(s), and lesion(s) are confirmed by histologic examination to be other than normal lung tissue.
2. Identification of one or more synchronous or occult lung lesions using VGT-309 with NIR imaging when standard surgical techniques using white light and/or palpation and preoperative imaging failed to identify the lesion(s), and lesion(s) are confirmed by histologic examination to be cancerous or precancerous.
3. Identification of fluorescence within  $\leq 10$  mm from the inside edge of the closest staple line as measured by the investigator *ex vivo* in the operating room using NIR imaging, with pathologic margin confirmed by histologic examination to be  $\leq 10$  mm.

NOTE: Margins from excisions of known or suspected metastases at the time of the surgery, OR diagnostic wedge resections where a completion lobectomy or segmentectomy was subsequently performed, will not be considered for Margin CSE inclusion.

4. Identification of lymph nodes by VGT-309 with NIR imaging confirmed by histologic examination to be cancerous.

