## **9. EFFICACY ANALYSES**

### **9.1. Definition of the Primary Efficacy Endpoint**

The proportion of subjects with at least one Clinically Significant Event (CSE) as defined by:

1. Intraoperative localization of one or more preoperatively identified lung lesions using VGT-309 with NIR imaging when standard surgical techniques using white light and/or palpation failed to identify the lesion(s), and lesion(s) are confirmed by histologic examination to be other than normal lung tissue.

2. Identification of one or more synchronous or occult lung lesions using VGT-309 with NIR imaging when standard surgical techniques using white light and/or palpation and preoperative imaging failed to identify the lesion(s), and lesion(s) are confirmed by histologic examination to be cancerous or precancerous.
3. Identification of fluorescence within  $\leq 10$  mm from the inside edge of the closest staple line as measured by the investigator *ex vivo* in the operating room using NIR imaging, with pathologic margin confirmed by histologic examination to be  $\leq 10$  mm. NOTE: Margins from excisions of known or suspected metastases at the time of the surgery, OR diagnostic wedge resections where a completion lobectomy or segmentectomy was subsequently performed, will not be considered for Margin CSE inclusion.
4. Identification of lymph nodes by VGT-309 with NIR imaging confirmed by histologic examination to be cancerous.

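### The margin event (CSE type C) requires no cancer, and its NOTE leaves in benign diagnostic wedges with no completion resection, so such a wedge can count as a primary-endpoint success

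*Protocol*

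**What the plan says.** The primary endpoint is the proportion of subjects with at least one of four CSE types. The definition stands in four places with the same content: the protocol synopsis, protocol 2.2.1 (A to D), and SAP 3.1 and 9.1 (items 1 to 4).

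For type C the histology condition in SAP 9.1 reads "with pathologic margin confirmed by histologic examination to be", and what follows is a distance of 10 mm or less. Type B, by contrast, requires that "lesion(s) are confirmed by histologic examination to be cancerous or precancerous".

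The NOTE to type C has two exclusions. One covers metastases known or suspected at the time of surgery. The other says that "diagnostic wedge resections where a completion lobectomy or segmentectomy was subsequently performed, will not be considered for Margin CSE inclusion".

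On eligibility, protocol 5.2 item 4 admits nodules that are not biopsy-proven. Item 5 asks the subject to "Be scheduled to undergo standard of care surgical resection for a lung nodule or mass with diagnostic and/or curative intent". The Evaluable Population (protocol 10.2, SAP 7.3.4) does not require malignant histology.

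On the decision rule, the synopsis states: "The trial will have met the primary endpoint if at least 15/86 (17.4%) subjects have at least one CSE".

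**The concern.** A close margin bears on cancer control only if the lesion is cancer or on the way to it. Types B and D build that in. Type A does not, but it says openly that any tissue other than normal lung qualifies, and only where standard technique failed to find the lesion. Type C has neither a tissue condition nor a failure-of-standard-technique condition.

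The NOTE does not repair this. It drops the diagnostic wedges that led to a larger resection and keeps those that did not. A nodule that turns out benign on wedge, with nothing further resected, falls in the group that is kept.

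The endpoints can then disagree about the same nodule. If it also fluoresces in vivo, it is a false positive in the secondary positive predictive value (PPV) and, with a close margin, a success in the primary endpoint. At stake is what a positive result would mean: the count that rejects the null could include margin events with no cancer present.

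**Working it through.** **Step 1. What histology must show for each CSE type**

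| Type | Required tissue result |
|---|---|
| A (pre-operatively identified lesion) | anything other than normal lung |
| B (synchronous or occult lesion) | cancer or precancer |
| C (margin) | none; a distance of 10 mm or less |
| D (lymph node) | cancer |

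No readable part of either document adds a tissue condition to type C. Protocol section 10 lets the SAP govern where the two differ, but the SAP repeats the definition. SAP 9.3 tabulates CSEs by type across lesion histopathology; that is descriptive and does not change who counts. The Data Review Committee in SAP 8.2 classifies protocol deviations and is not described as adjudicating CSEs.

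**Step 2. Reproduce the plan's figures**

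The inputs come from the synopsis (Statistical Methods): "assuming a 20% true rate of at least one CSE, two-sided 5% Type 1 error and 80% power", with p0 = 0.10, p1 = 0.20 and n = 86. Protocol 10.3.2 and SAP 9.3 specify an exact binomial test at one-sided 0.025.

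- Sample size by normal approximation: ((1.960 × √(0.10 × 0.90) + 0.842 × √(0.20 × 0.80)) / 0.10)² = 85.5, rounded up to 86. This reproduces.
- Clopper-Pearson interval at 15/86 = 17.4%: 10.1% to 27.1%. This reproduces.
- P(X ≥ 15 | 86, 0.10) = 0.023, within 0.025. P(X ≥ 14 | 86, 0.10) = 0.046, above 0.025. So 15 is the correct minimum.
- Exact power of the rule, P(X ≥ 15 | 86, 0.20) = 76.3%. The stated 80% belongs to the normal approximation. The power figures in step 5 start from 76.3%.

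**Step 3. Effect of one subject (no assumed rates)**

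Suppose exactly 15 of 86 subjects succeed and, for one of them, the only CSE is a benign margin. With a cancer condition that subject stays in the denominator and leaves the numerator:

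- 15/86 = 17.4%, lower bound 10.1%, p = 0.023: met.
- 14/86 = 16.3%, lower bound 9.2%, p = 0.046: not met.

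**Step 4. Illustration of size (assumed rates)**

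Assume that all other CSEs together occur in exactly 10% of subjects, and that a further b percentage points of subjects have a benign margin as their only CSE. The chance of meeting the rule is P(X ≥ 15 | 86, 0.10 + b).

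| b (points) | Composite rate | P(at least 15/86) |
|---|---|---|
| 0 | 10% | 2.3% |
| 1 | 11% | 4.8% |
| 2 | 12% | 8.7% |
| 3 | 13% | 14.4% |
| 5 | 15% | 30.5% |

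**Step 5. Power after a fix, if the planned 20% included such events**

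Removing b points leaves a true rate of 0.20 − b. Exact power falls from 76.3% to 68.6%, 59.7%, 50.1% or 30.5% for b = 1, 2, 3 or 5 points.

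**The case against.** Several arguments run the other way.

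- **The test is not in error.** The null hypothesis concerns the composite as defined. If benign margins are CSEs, a composite rate of 15% is truly above 10% and rejecting is correct. A reader might take the table in step 4 as type I error inflation. It is not: the exact size of the rule remains 0.023. This stands.
- **Benign tissue is not foreign to the endpoint.** The primary objective is lesion visualization, and type A accepts benign lesions. This stands in part. Type A does so expressly and only where standard technique failed; type C is silent and has no such condition.
- **The secondary PPV is read in vivo.** A reader might infer that every benign margin event is also a false positive there. The documents do not support that. Type C is measured ex vivo, ex vivo PPV is exploratory (SAP 9.5), and the conflict arises only when the nodule also fluoresces in vivo.
- **Benign margins may never be scored.** Neither document defines the pathologic margin. A site might read it as a tumour margin, or report none for a benign lesion, and the Pathology Manual is not among the documents. So the text supports saying that benign wedges can count, not that they will. The primary endpoint would still depend on local reading.
- **The size is assumption-driven.** With a 20% benign share, half of those meeting both distances, and other CSEs at 10%, the composite is 0.10 + 0.9 × 0.20 × 0.50 = 19.0% and P(at least 15/86) is 69%. With 10% and 10% it is 0.10 + 0.9 × 0.10 × 0.10 = 10.9% and 4.5%. The documents anchor neither pair, so no particular inflation can be claimed.

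**Conclusion.** The gap is real and stands in all four copies of the definition. As written, a fluorescing benign nodule removed by diagnostic wedge without completion resection can be a primary-endpoint success if both distances are 10 mm or less.

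The firm part of its size needs no assumed rates: the rule sits at its limit, so one benign margin-only subject can turn 14/86 into 15/86 and a missed endpoint into a met one. The 4.8% to 30.5% range is an illustration only. It rests on other CSEs being at exactly 10% and on 1 to 5 assumed points of benign margin-only subjects.

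The harm is to the interpretation of a rejection, not to the validity of the test. How often it would happen cannot be derived from the documents.

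**What to change.** - In the synopsis, protocol 2.2.1 C, and item 3 of SAP 3.1 and 9.1, add to type C that the lesion whose margin is measured must be shown on histology to be cancer or precancer, matching type B. Keep the NOTE as it is.
- Do not narrow the condition to primary lung cancer. That would also remove metastases unsuspected at surgery, which the NOTE leaves eligible, and precancerous lesions, which type B accepts. Nothing in this point justifies either removal.
- Define the pathologic margin as the distance from that lesion to the staple line.
- Report the primary result with and without benign margin-only CSEs as a sensitivity analysis.

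The cost is a short change to the endpoint text of both documents. Resected tissue already goes to histology (protocol 8.1 and 8.4), and SAP 9.3 already tabulates CSEs by lesion histopathology, so no new data are needed. The downside is a possibly lower CSE count. If the planned 20% rate included benign margin events, power falls as in step 5 and the choice of 86 evaluable subjects should be looked at again.
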